#### 11.2.4 Concomitant medications Data

This dataset regroups information from Concomitant/Prior Medications (CM) and its supplemental domain, in an Occurrence Data Structure (OCCDS).

**Previous therapy flag** is equal to Y when the therapy is reported on the corresponding eCRF 'Previous Non SLE Therapies' page (corresponds to Category equal to 'GENERAL' and Subcategory equal to 'PRIOR')

**Concomitant therapy flag** is equal to Y when the therapy is reported on the corresponding eCRF 'Concomitant Medication' page (Category equal to 'GENERAL' and Subcategory equal to 'CONCOMITANT')

**Previous SLE therapies flag** is equal to Y when the therapy is reported on the corresponding eCRF 'Previous SLE Therapies' page (Category equal to 'SLE SPECIFIC' and Subcategory equal to 'PRIOR')

**Concomitant (Background) SLE therapy flag** is equal to Y when the therapy is reported on the corresponding eCRF 'Background SLE Therapies' page (Category equal to 'SLE SPECIFIC' and Subcategory equal to 'CONCOMITANT')

### 11.2.5 Study treatment exposure and compliance

#### 11.2.5.1 Exposure

This dataset regroups information from Exposure (EX) Domain and its supplemental domain, in a Basic Data Structure (BDS).

The following parameters are defined:

**Re-initiation performed** is defined to Y if there is more than one record in the EX domain with Group ID equals to 'DAY 1 /RE-INITIATION', equals to N otherwise.

**Study treatment duration (days)** is defined as the number of days between start of study treatment and permanent treatment discontinuation of study treatment (both inclusive), regardless of interruption, i.e.,

Latest end date of Treatment - Earliest start date of treatment intake +1.

It is also categorized as (non-exclusive mutually): at least 1 day, at least 1 week (7 days), at least 4 weeks (28 days), at least 8 weeks (56 days) and at least 11 weeks (77 days).

**Study treatment duration (days)**, excluding interruptions, is defined as the total number of days of all treatment intervals (end date of interval minus start date of interval + 1 [in days], excluding overlaps).

#### 11.2.5.2 Compliance (based on drug accountability)

This dataset regroups information from Drug Accountability (DA) Domain and its supplemental domain, in a Basic Data Structure (BDS).

### 11.2.6 Pharmacodynamic data

This dataset contains information from Laboratory Test Findings (LB) domain in a BD structure. It is limited to the parameter named 'Lymphocyte' as measured by the central laboratory.

**Baseline, Absolute value at each post-baseline assessment, Absolute and percent change from baseline to each post-baseline assessment** variables are populated as described in the general section.

### 11.2.7 Adverse event data

This dataset contains information from Adverse Events (AE), its supplemental domain and Healthcare Encounters (HO) domain in an Occurrence Data Structure.

Events are considered '**Pre-treatment**' if the onset date is prior to the date of first study treatment intake or if it occurs on the day of the intake when the answer to 'Did this adverse event start at visit 2 or on first day of re-initiation following study drug intake?' is equal to 'No'.

Events are considered '**With onset on day 1**' if the onset date is equal to the first study treatment intake and the answer to 'Did this adverse event start at visit 2 or on first day of re-initiation following study drug intake? ' is answered 'Yes'.

Events are considered '**With onset after day 1**' if the onset date is later than the first study treatment intake.

Events are considered '**Treatment Emergent**' if the onset date is equal to the first study treatment intake and the answer to 'Did this adverse event start at visit 2 or on first day of re-initiation following study drug intake? ' is answered 'Yes' or if the onset date is later than the study treatment intake.

**Analysis Severity/Intensity** is derived if there are missing values in the original SDTM variable. If the original value is missing, it is imputed as 'SEVERE'.

**Analysis Causality** is defined as equal to the Causality recorded in the original SDTM variable as RELATED/ NOT RELATED. If the original value is missing, it is imputed as RELATED.

For serious adverse events requiring or prolonging hospitalization, the following variables are populated: Hospitalization Start Date, Hospitalization End Date, Hospitalization Start Relative Day, Hospitalization End Relative Day.

Events are considered '**Adverse events leading to discontinuation of study treatment**' when action taken with study treatment is recorded as 'permanently discontinued' on the Adverse Event eCRF (in the original SDTM variable 'DRUG WITHDRAWN').

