#### **11.4.3 Analysis of the safety variable(s)**

The Safety Analysis Set will be used to perform all safety analyses.

If not otherwise stated, only treatment-emergent safety data (observations with onset or assessment dates at/after first intake of study drug up to 6 weeks after study drug discontinuation) will be considered in tables and figures. All safety data will be included in listings, with flags for safety data not considered to be treatment-emergent.

Specific safety events (AEs, laboratory tests, ECG findings, etc.) will be considered. In general, they consist of one or more well-defined safety events that are similar in nature and for which there is a specific clinical interest in connection with ACT-334441.

For specific AESIs, the number and percentage of subjects with at least one event will be reported. Point estimates and 95% CIs for safety-event incidences and the relative risk ratio relative to placebo will be provided without adjustment for multiplicity.

Exploratory analysis of time to first onset of safety events of interest may be displayed by Kaplan-Meier estimates. Subjects not experiencing the safety event will be censored at the minimum of the EOS date and 6 weeks after last dose of study drug. Where applicable, study treatment doses will be compared with placebo by hazard ratios and corresponding 95% CIs from Cox's regression model.

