#### 5.8.1.1 *Treatment-emergent adverse events*

A treatment-emergent adverse event (TEAE) is any AE temporally associated with the use of study treatment (from study treatment initiation until Visit 7 [EOS]) irrespective whether considered by the investigator to be related to study treatment or not.

An AE is considered a TEAE if the start date is after (>) the first study treatment intake or the start date is on the same day as the first study treatment intake and the answer to 'Did this adverse event start at visit 2 or on first day of re-initiation following study drug intake?' is equal to 'Yes' indicating that the AE started after first intake of study treatment.

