### 5.8.3 Serious adverse events

An AE is considered serious if the investigator ticked ‘Yes’ on the question ‘Serious?’ on the Adverse Event eCRF or if it is missing.

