### 5.8.5 Other significant adverse events

#### 5.8.5.1 AE of special interest

An AE is considered to be an AE of special interest (AESI) if it is treatment emergent and belongs to any of the categories listed below (the list of corresponding MedDRA PT is defined in the latest AESI list enclosed in [Appendix 15.2.2](#)):

- Effect on heart rate and rhythm AESI (including hypotension)
- Cardiovascular AESI
- Hypertension AESI
- Liver AESI (Hepatobiliary disorders/ liver enzyme abnormality)
- Pulmonary AESI
- Macular edema AESI
- Infection AESI
- Herpetic infections AESI
- Skin malignancy AESI
- Non-Skin malignancy AESI
- Stroke AESI
- Seizure AESI

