## 11.2 Analysis variables

### 11.2.1 General

**Baseline value** is defined as the last non-missing value before date and time of first dose intake of double-blind treatment.

**Analysis value** is defined as the value at the visit (numeric result in standard units).

**Absolute change from baseline** is defined as post-baseline value minus baseline value, i.e., a positive sign indicates an increase as compared to baseline.

**Percent change from baseline** is defined as the absolute change from baseline divided by the baseline value (if the baseline value is  $> 0$ ) and then multiplied by 100.

**Ratio to baseline** is defined as the value at the visit divided by the value at baseline (if the baseline value is  $> 0$ ).

**Analysis Date** is defined as the numeric SAS date derived from the Date/Time of assessment. It can be an imputed date [cf. section 12 for more details].

**Analysis Start Date** is defined as the numeric SAS date derived from the Start Date/Time of an event. It can be an imputed date [cf. section 12 for more details].

**Analysis End Date** is defined as the numeric SAS date derived from the End Date/Time of an event. It can be an imputed date [cf. section 12 for more details].

**Analysis End Relative Day** is estimated for several assessments, including AE end, treatment interruptions, concomitant medication end. It refers to the number of days between the end of the specific event and the first study treatment intake.

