### 12 HANDLING OF MISSING/INCOMPLETE DATE AND TIME FIELDS

This section describes some general principles to be followed in the case of missing or incomplete dates/times. Missing parts for specific dates/times are changed into acceptable non-missing values as described in the below [Table 15](#).

**Table 15** Handling of missing date and time

| Type of date/time                                      | Imputation method when date/time is incomplete   | Imputation method when date/time is missing |
|--|--|---|
| Start of study treatment
(Randomized subjects only) | Day is missing (i.e., "yyyy.mm")
Whichever is the later of "yyyy mm.01" or the date of randomization
Day and month are missing (i.e., "yyyy")
Whichever is the later of "yyyy.01.01" or the date of randomization | Date of randomization (IVRS)                |
| End of study treatment
(Randomized subjects only)   | Day is missing (i.e., "yyyy.mm")
Whichever is the earlier of "yyyy mm.28/29/30/31" and the Visit 6 (EOT) date  | Date of V6 - (Premature) End of Treatment   |

| Type of date/time  | Imputation method when date/time is incomplete  | Imputation method when date/time is missing                       |
|--|---|---|
| Start Date of Adverse Event
(Randomized subjects only) | 
Day and month are missing (i.e., "yyyy")
                     Whichever is the earlier of "yyyy.12.31" and the Visit 6 (EOT) date
 
Day is missing (i.e., "yyyy.mm")
                     If month and year of the episode = month and year of first study treatment intake then
                         Start date=date of first study treatment intake,
                         otherwise
                         Start date= yyyy.mm.01
 
Day and month are missing (i.e., "yyyy")
                     If year of the episode = year of first study treatment intake then
                         Start date = date of first study treatment intake,
                         otherwise
                         Start date= yyyy.01.01
 | Date of first study treatment intake                              |

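### Adverse events whose missing start date is imputed to the first-dose day drop out of the treatment-emergent tables unless one eCRF question is answered 'Yes'

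*SAP*

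**What the plan says.** Four rules act together.

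- **Imputation (SAP 12, Table 15).** An AE start date becomes the date of first intake in three cases: the whole date is missing; day and month are missing and the year matches; or only the day is missing and both month and year match ("If month and year of the episode = month and year of first study treatment intake then" the start date is the intake date). Other partial dates go to the first day of the known month or year.
- **Use of imputed dates (SAP 11.2.1).** Of the analysis start date it says: "It can be an imputed date [cf. section 12 for more details".
- **Classification (SAP 5.8.1.1 and 11.2.7).** An AE dated after first intake is treatment-emergent. One dated on the intake day is treatment-emergent only if "the start date is on the same day as the first study treatment intake and the answer to" the eCRF question on onset at Visit 2 or the first re-initiation day, following drug intake, is 'Yes'. Under 11.2.7 an AE is pre-treatment "if it occurs on the day of the intake when the answer to" that question is 'No'.
- **Downstream use (SAP 5.8.5.1).** An AE is an AESI only "if it is treatment emergent and belongs to any of the categories listed below".

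Protocol 11.4.3 describes treatment-emergent data as "observations with onset or assessment dates at/after first intake of study drug up to 6 weeks after study drug discontinuation".

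**The concern.** The eCRF question asks about particular days. For a complete onset date equal to the first-dose date, 'No' sensibly means before the dose. For a date that was only imputed to that day, 'No' may equally mean some later day, yet the SAP reads it as pre-treatment. Nothing in the SAP exempts imputed dates from the same-day question.

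For these AEs the rule works against detecting harm, and safety and tolerability is one of the two main objectives. Affected AEs leave the tables of treatment-emergent AEs, treatment-emergent SAEs, treatment-emergent AEs leading to discontinuation, and AESIs. The SAP handles other missing AE attributes the opposite way. For causality, "If the original value is missing, it is imputed as RELATED". Missing intensity becomes severe. An AE is serious if so ticked "on the Adverse Event eCRF or if it is missing".

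**Working it through.** The plan gives no figure of its own to reproduce, so the check applies the rules as written.

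**Rule trace, illustrative first dose 3 May**

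| Recorded onset | True onset | Answer | Imputed to | Class |
|---|---|---|---|---|
| day missing, May | 9 May | 'No' | 3 May | pre-treatment (lost) |
| day missing, May | 9 May | blank | 3 May | neither (lost) |
| day missing, May | 9 May | 'Yes' | 3 May | treatment-emergent |
| day missing, June | in June | any | 1 June | treatment-emergent |

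**All onset days.** Inputs: 12 weeks of dosing (84 days) plus 6 weeks (42 days) gives a window ending on Day 126, so Days 2 to 126 hold 125 possible onset days after Day 1. The first-dose dates are illustrative. The table shows the days lost when the answer is 'No'.

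| First dose | Complete date | Day missing | Day and month missing | Wholly missing |
|---|---|---|---|---|
| 1 March 2016 | 0/125 | 30/125 | 125/125 | 125/125 |
| 15 March 2016 | 0/125 | 16/125 | 125/125 | 125/125 |
| 31 March 2016 | 0/125 | 0/125 | 125/125 | 125/125 |
| 15 October 2016 | 0/125 | 16/125 | 77/125 | 125/125 |

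With a blank answer the same days are lost, but the AE is unclassified rather than pre-treatment. With 'Yes' nothing is lost.

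**Averages.** These take every first-dose date in 2015 and 2016 (731 dates, assumed equally likely; the years serve only as a calendar):

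- Day missing: a mean of 14.7 window days fall in the first-dose month, 14.7/125 = 11.8%. The range is 0 to 30 days, at most 30/125 = 24%.
- Day missing, Days 2 to 14 only: a mean of 10.0 of 13 days, 77.0%.
- Day and month missing: a mean of 103.5 of 125 days fall in the first-dose year, 82.8%.
- Wholly missing: 125/125 = 100%.

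These are shares of calendar days within each missing-date pattern. They are not shares of AEs.

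**Effect on a table cell.** With the planned 12 subjects per active arm and 12 + 4 = 16 on pooled placebo, one lost subject changes an incidence by at most 1/12 = 8.3 points or 1/16 = 6.25 points, and only if that subject has no other event in the row.

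**The case against.** The strongest objection is that the harm depends on facts outside the documents. It needs an incomplete start date still unresolved at database closure, in a pattern that imputes to first intake, with an answer other than 'Yes'. The eCRF completion logic is not shown. AEs are collected at every visit, queries run until closure, and SAEs also go on a separate form within 24 hours. This stands as a limit on size: the number could be zero. It does not repair the rule, which should not rely on every date being resolved.

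A second objection is that protocol 11.4.3 does not mention imputed dates and that the protocol leaves derivations to the SAP, so this is a gap between two rules rather than a contradiction. That is partly fair. Still, for these AEs the result departs from onset at or after first intake, and the SAP's section on changes and clarifications does not mention it.

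Third, the worst-case defaults apply to missing values, whereas 'No' is a recorded answer. This is true for 'No'; the comparison is exact only for a blank. But the missing item here is the onset date, and 'No' does not establish that onset came before dosing.

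Fourth, the remedy has a cost of its own. AEs are collected from consent, up to 30 days before Day 1. On the same calendar assumption, a mean of 14.7 of those 30 days (49%) fall in the first-dose month, so an ongoing screening AE with a missing day would be counted as treatment-emergent. This stands and is weighed under the fix.

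Finally, all AEs remain in the listings with a treatment-emergent flag. SAEs and AEs leading to discontinuation have their own listings, and deaths after the start of treatment are tabulated without that flag. A misclassified AE could therefore be spotted, but the summary tables would still be wrong.

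**Conclusion.** The concern holds. Read as written, the SAP removes from the treatment-emergent and AESI tables any AE that began after Day 1, whose start date is imputed to first intake, and whose eCRF answer is not 'Yes'. Reading onset date as the raw recorded date does not rescue a wholly missing date, which then meets neither treatment-emergent condition.

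The number of such AEs is unknown. The calendar shares in the check rest on an even spread of first doses, 84 days of dosing and 42 days of follow-up. Where only the day is missing, about 88% of the window is safe, and the exposure is concentrated in the first two weeks. Complete dates, partial dates in a later month or year, and 'Yes' answers are handled correctly, and a true screening AE answered 'No' is rightly kept out.

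This should be fixed because safety is a main objective and the arms are small. It does not touch the lymphocyte analysis.

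**What to change.** In SAP 5.8.1.1 and 11.2.7, apply the Visit 2/re-initiation question only when the recorded onset date is complete and equals the first-intake date. Where the onset date was imputed to first intake, or the answer is blank for a same-day onset, class the AE as treatment-emergent unless the known date parts or a recorded end date show that it began or ended before first intake. In practice the end date will do most of this work, because a partial date imputed to first intake agrees with it in every part that is known.

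With this change all 125 of 125 onset days after Day 1 are treatment-emergent in every missing-date pattern, as protocol 11.4.3 implies.

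The cost is two sentences and one programming condition. The downside is that some screening AEs with incomplete start dates and no end date before dosing will be counted as treatment-emergent. That error is conservative and in keeping with the SAP's other rules for missing AE data.

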#### ***Adverse Events of special interest (AESI)***

The definitions for adverse events of special interest are based on systematic approach using Standardized MedDRA Queries (SMQ). The current proposal is based on S1P1 projects\_AESI\_definitions\_MedDRA version 19.0\_09Sep2016. The following safety areas are addressed by the pre-defined adverse events of special interest:

| Protocol wording   | Excel Sheet Name               | Criterion name                     | Criterion label   |
|--|--------------------------------|------------------------------------|---|
| Effect on HR and rhythm related AEs
Hypotension related AEs | Bradyarrhythmia
Hypotension | AESI01FL+
AESI02FL=
AESI14FL | Bradyarrhythmia flag +
Hypotension flag
= Effect on heart rate and
rhythm flag |
| Cardiovascular related AEs                                     | Cardiovascular                 | AESI03FL                           | Cardiovascular flag   |

| Protocol wording  | Excel Sheet Name      | Criterion name | Criterion label                       |
|---|-----------------------|----------------|---------------------------------------|
| Hypertension related AEs                                      | Hypertension          | AESI04FL       | Hypertension flag                     |
| Hepatobiliary disorders /liver enzyme abnormality related AEs | Liver                 | AESI05FL       | Liver flag                            |
| Pulmonary related AEs   | Pulmonary             | AESI06FL       | Pulmonary flag                        |
| Eye disorders related AEs                                     | Macular edema         | AESI07FL       | Macular edema flag                    |
| Infection related AEs   | Infections            | AESI13FL       | Infection (if serious or severe) flag |
| Missing/ New  | Herpetic infection    | AESI08FL       | Herpetic infection flag               |
| Skin malignancy related AEs                                   | Skin malignancies     | AESI09FL       | Skin malignancy flag                  |
| Non-Skin malignancy related AEs                               | Non-skin malignancies | AESI10FL       | Non-skin malignancy flag              |
| Missing/ New  | Stroke                | AESI11FL       | Stroke flag                           |
| Missing/ New  | Seizures              | AESI12FL       | Seizure flag                          |

### 11.2.8 Medical history data (general)

This dataset contains information from Medical History (MH) Domain, its supplemental domain, in an occurrence data structure. It is restricted to the records with category equal to GENERAL.

For diseases and diagnoses, an additional **End Reference Time Point** is set up to 'START OF TREATMENT'.

For **previous medical history**, the **End Relative to Reference Time Point** is equal to BEFORE.

For **concomitant medical history**, the **End Relative to Reference Time Point** is equal to ONGOING.

### 11.2.9 Medical history data, SLE specific

This dataset contains information from Medical History (MH) Domain (restricted to category equal to SYSTEMIC LUPUS ERYTHEMATOSUS RELEVANT DISEASE HISTORY) and its supplemental domain, in a basic data structure.

Each criterion is mapped into a parameter. The analysis value is equal to the occurrence of the pre-specified event.

In addition, the following parameters are derived:

- **Time from first SLE symptoms (years) to informed consent signature** is calculated as follows: (Informed consent date - date of first symptoms)/365.25.

- **Time from SLE diagnosis (years) to informed consent signature** is calculated as follows: (Informed consent date - date of SLE diagnosis)/365.25.
- **Number of SLE symptoms** according to ACR criteria [ACR 1997] **met in the past** is calculated for each subject as the number of observations with Event Pre-Specified equal to Y and Occurrence equal to Y and End Relative to Reference Time Point equal to BEFORE.
- **Number of SLE symptoms** according to ACR criteria [ACR 1997] **started more than 6 months prior to screening** is calculated for each subject as the number of observations with Event Pre-Specified equal to Y and Occurrence equal to Y and Did it start more than 6 months prior? equal to Y.
- **Number of SLE symptoms** according to ACR criteria [ACR 1997] **ongoing at screening** is calculated for each subject as the number of observations with Event Pre-Specified equal to Y and Occurrence equal to Y and End Relative to Reference Time Point equal to ONGOING.
- **Number of SLE symptoms** according to ACR criteria [ACR 1997] **met either serially or simultaneously** is calculated for each subject as the number of observations with Event Pre-Specified equal to Y and Occurrence equal to Y.

For each **Number of SLE symptoms** computed, the analysis value is further categorized in 0-3 and 4-11.

- **Presence of a documented historical positive ANA** is equal to Y when there is at least one observation in LB Domain with Group ID equal to 'PREVIOUS TESTINGS' and Lab Test or Examination Short Name equal to 'ANA'.
- **Presence of a documented historical positive anti-dsDNA** is equal to Y when there is least one observation in LB Domain with Group ID equal to 'PREVIOUS TESTINGS' and Lab Test or Examination Short Name equal to 'ADSDNA'.

